8. Change from baseline in the Timed Up and Go (TUG) test time at Month 3 and annual visits, at each Unscheduled Injection Visit, and 3 months after each injection (at a subset of sites)
9. Frequency of and interval between knee IA injections

Methodology: This study will be a multicenter, open-label study. Up to 300 subjects will be enrolled. After a screening period of up to 14 days, subjects will receive an IA injection of 0.07 mg LOR into one or both knees, followed by a 36-month evaluation period. Clinic visits will be scheduled at Day 1, and Months 3, 12, 24, and 36 (End of study [EOS]) or Early Termination (ET) for completion of all PRO measurements (WOMAC, KOOS, pain NRS, SF-12, PASS, WPAI), functional tests (40-meter walk test and TUG test at a subset of sites), and safety evaluations. On Day 1, the Charlson Comorbidity Index and Widespread Pain Index and Symptom Severity [WPI&SS] assessments will also be completed. A phone visit for safety follow-up will occur 4 weeks after the injection on Day 1. Refer to [Figure 1](#) for an overview of the study design. Subjects may also have Unscheduled Injection Visits for additional injections of LOR, glucocorticoid, or HA, as described in the OA Treatment Algorithm section below. Following each injection, subjects will return to the clinic for 3-Month Post-Injection Follow-Up Visits, unless another visit has occurred between the injection and the 3-month post injection date. At these injection visits and 3-Month Post-Injection Follow-Up Visits, subjects will complete PRO measurements and functional tests (at a subset of sites).

Mode of Administration: Direct IA injection into one or both knee joints. LOR injections into the same knee must be separated by at least 6 months; glucocorticoid and HA injections must be performed in accordance with US prescribing information (USPI).

OA Treatment Algorithm:

LOR Injections:

- On Day 1, after subject eligibility has been confirmed and subjects complete all PRO measurements and functional tests (at applicable sites), subjects will receive an IA injection of 0.07 mg LOR into one or both knees. Bilateral injections of 0.07 mg LOR are allowed.
- Subjects may receive additional injections of LOR into one or both knees, as clinically indicated, at any time between Day 1 and Month 33 with the restriction that LOR injections into the same knee must be separated by at least 6 months; these injections can

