3.2.2 EFFICACY ENDPOINTS

1. Change from baseline in pain numeric rating scale (NRS) score for the knee at Month 3 and annual visits, at each Unscheduled Injection Visit, and 3 months after each injection
2. Change from baseline in Western Ontario and McMaster Universities Osteoarthritis Index (WOMAC) physical function subscore (WOMAC Function) at Month 3 and annual visits, at each Unscheduled Injection Visit, and 3 months after each injection
3. Change from baseline in WOMAC total score and pain and stiffness subscores at Month 3 and annual visits, at each Unscheduled Injection Visit, and 3 months after each injection
4. Change from baseline in the Knee Injury and Osteoarthritis Outcome Score (KOOS) subscales of Symptoms, Function (Sports), and Quality of Life at Month 3 and annual visits, at each Unscheduled Injection Visit, and 3 months after each injection
5. Change from baseline in HRQoL (as measured using the 12-Item Short Form Health Survey [SF-12]) and Work Productivity and Activity Impairment (WPAI) at Month 3 and annual visits
6. Patient-Acceptable Symptom State (PASS) at Month 3 and annual visits
7. Change from baseline in 40-meter walk test time at Month 3 and annual visits, at each Unscheduled Injection Visit, and 3 months after each injection (at a subset of sites)
8. Change from baseline in the Timed Up and Go (TUG) test time at Month 3 and annual visits, at each Unscheduled Injection Visit, and 3 months after each injection (at a subset of sites)
9. Frequency of and interval between knee IA injections

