4. STUDY DESIGN

4.1 DESCRIPTION OF THE STUDY DESIGN

This study will be a multicenter, open-label study. Up to 300 subjects will be enrolled. After a screening period of up to 14 days, subjects will receive an IA injection of 0.07 mg LOR into one or both knees, followed by a 36-month evaluation period. Clinic visits will be scheduled at Day 1, and Months 3, 12, 24, and 36 (End of study [EOS]) or Early Termination (ET) for completion of all PRO measurements (WOMAC, KOOS, pain NRS, SF-12, PASS, WPAI), functional tests (40-meter walk test and TUG test at a subset of sites), and safety evaluations. On Day 1, the Charlson Comorbidity Index and Widespread Pain Index and Symptom Severity [WPI&SS] assessments will also be completed. A phone visit for safety follow-up will occur 4 weeks after the injection on Day 1. Refer to [Figure 1](#) for an overview of the study design. Subjects may also have Unscheduled Injection Visits for additional injections of LOR, glucocorticoid, or HA, as described in the OA Treatment Algorithm section below. Following each injection, subjects will return to the clinic for 3-Month Post-Injection Follow-Up Visits, unless another visit has

occurred between the injection and the 3-month post injection date. At these injection visits and 3-Month Post-Injection Follow-Up Visits, subjects will complete PRO measurements and functional tests (at a subset of sites). Specific timing of protocol procedures is described in the Schedule of Events Table ([Section 7.3.7](#)).

This study will be conducted at approximately 30 investigational centers.

Recording of AEs will start following study injection on Day 1 and continue at all subsequent in-person and phone visits until the subject completes Month 36 (EOS)/ET. All AEs, whether volunteered, elicited, or noted during examination, will be recorded throughout the study.

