- Following each injection that occurs at or after the Month 3 visit, subjects will return to the clinic for a 3-Month Post-Injection Follow-Up Visit unless another visit has occurred between the injection and the 3-month post-injection date.
 - If a subject receives a glucocorticoid or HA injection for the indication of OA at a location different than the study site, a 3-Month Post-Injection Follow-Up Visit should be scheduled unless another visit has occurred between the injection and the 3-month post-injection date.
 - For subjects who receive HA as a series of injections, the first visit will be used to determine when the 3-Month Post-Injection Follow-Up Visit should occur.
- Bilateral injections are allowed and may occur at the same visit, but only one injection per knee can occur at any visit.
- Prior to the injection(s), the Investigator should evaluate the subject for suitability to receive the injection(s). The subject should not have any condition that, in the opinion of the Investigator, constitutes a risk or contraindication for the injection(s).
- Any knee that has undergone a partial or total knee replacement should not be injected.

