7.3.4 ADDITIONAL VISITS

Unscheduled Injection Visit

Subjects may have Unscheduled Injection Visits at any time for additional injections of LOR (between Day 1 and Month 33) or glucocorticoid or HA (between Month 3 and Month 33) into one or both knees as clinically indicated. Refer to [Section 4.1.1](#) for restrictions and guidelines.

The following procedures and assessments will be performed at this visit:

- Collection of AE and concomitant procedures/therapies/medication data
- Knee examination of both knees
- Vital sign measurements (temperature, pulse rate, and blood pressure)
- WOMAC questionnaire
- KOOS questionnaire
- Pain NRS
- 40-meter walk test (at a subset of sites)
- TUG test (at a subset of sites)
- IA injection of LOR, glucocorticoid, or HA into the knee(s)

Note: PRO measurements (WOMAC, KOOS, and pain NRS) and functional tests (40-meter walk test and TUG test) do not need to be completed at this visit if they were completed within 2 weeks prior.

3-Month Post-Injection Follow-Up Visit

This visit should occur 90 days after any Unscheduled Injection Visit or after any IA glucocorticoid or HA injection occurring at a location different than the study site (with a window of ± 14 days) unless another visit has occurred between the injection and the 3-month post injection date.

The following procedures and assessments will be performed at this visit:

- Collection of AE and concomitant procedures/therapies/medication data
- Knee examination of both knees
- Vital sign measurements (temperature, pulse rate, and blood pressure)
- WOMAC questionnaire

- KOOS questionnaire
- Pain NRS
- 40-meter walk test (at a subset of sites)
- TUG test (at a subset of sites)

Once all study assessments are completed, and if clinically indicated, subjects may receive an injection of LOR, glucocorticoid, or HA into one or both knees. Refer to [Section 4.1.1](#) for restrictions and guidelines.

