7.3.7 SCHEDULE OF EVENTS TABLE

Schedule of Study Procedures	Screening (Day -14 to Day -1)	Day 1^a	Month 1 (Phone) (Day 30 ± 7 days)	Month 3 (Day 90 ± 14 days)	Months 12 and 24 (Days 360 and 720 ± 28 days)	Unscheduled Injection Visit^b	3-Month Post- Injection Follow-Up Visit^c (± 14 days)	Month 36 (EOS) (Day 1080 ± 28 days)/ ET^d
Informed consent	X							
Inclusion & exclusion criteria	X	X						
Demographics	X							
Medical history	X							X ^e
Current and prior procedures/medications	X	X						
Past treatments for knee OA pain	X							
Pregnancy test ^f	X	X						X
Urine drug test	X							
Injection into knee ^g		X ^h				X		
Physical examination	X	X			X			X
Knee examination	X	X		X	X	X	X	X
Weight	X				X			X
Height	X							
Vital signs	X	X		X	X	X	X	X
Clinical laboratory sampling	X				X			X
WPI&SS		X						
Charlson Comorbidity Index		X						
WOMAC		X		X	X	X	X	X
KOOS		X		X	X	X	X	X
Pain NRS		X		X	X	X	X	X

Schedule of Study Procedures	Screening (Day -14 to Day -1)	Day 1^a	Month 1 (Phone) (Day 30 ± 7 days)	Month 3 (Day 90 ± 14 days)	Months 12 and 24 (Days 360 and 720 ± 28 days)	Unscheduled Injection Visit^b	3-Month Post- Injection Follow-Up Visit^c (± 14 days)	Month 36 (EOS) (Day 1080 ± 28 days)/ ET^d
SF-12		X		X	X			X
PASS Question		X		X	X			X
WPAI		X		X	X			X
40-meter walk test ⁱ		X		X	X	X	X	X
TUG test ⁱ		X		X	X	X	X	X
AEs & concomitant procedures/ therapies/medications		X	X	X	X	X	X	X

- ^a All Day 1 procedures should be performed prior to study medication injection except for collection of AE and concomitant procedures/medication data.
- ^b The Unscheduled Injection Visit may only occur between Day 1 and Month 33 if the subject is receiving an IA LOR injection, or between Month 3 and Month 33 if the subject is receiving an IA glucocorticoid or HA injection. PRO measurements (WOMAC, KOOS, and pain NRS) and functional tests (40-meter walk test and TUG test) do not need to be completed at the Unscheduled Injection Visit if they were completed within 2 weeks prior.
- ^c This visit should occur 90 days after the Unscheduled Injection Visit or any IA glucocorticoid or HA injection occurring at a location different than the study site (with a window of ± 14 days) unless another visit has occurred between the injection and the 3-month post injection date.

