- ^d If possible, the ET visit should be performed within 14 days of subject premature withdrawal or termination. PRO measurements (WOMAC, KOOS, pain NRS, SF-12, PASS, WPAI) and functional tests (40-meter walk test and TUG test) do not need to be completed at the ET visit if they were completed within 2 weeks prior.
- ^e Review medical history to capture End Date(s), if applicable, of any ongoing medical history(ies) collected at the Screening Visit.
- ^f A serum pregnancy test will be performed on WOCBP at the Screening visit and a urine pregnancy test will be performed on WOCBP at Day 1 and Month 36 (EOS)/ET.
- ^g At Unscheduled Injection Visits, 3-Month Post-Injection Follow-Up Visits, or at Months 3, 12, or 24 (after completion of all visit assessments), subjects may receive LOR, glucocorticoid, or HA in either knee. Refer to the OA Treatment Algorithm in [Section 4.1.1](#) for further details.
- ^h Subjects are to receive an IA injection of LOR into one or both knees on Day 1.
- ⁱ Functional tests will only be performed at a subset of sites.
- ^j For any subjects who have a total or partial knee replacement of the knee diagnosed with OA in unilateral OA or of either knee in bilateral OA, sites should follow up with these subjects approximately 6 months after the total or partial knee replacement surgery is completed to assess outcomes of the surgery.

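### Protocol 7.3.4 and Schedule of Events footnote c plan no 3-month visit after injections given at Months 3, 12 and 24 or at follow-up visits, although 4.1, 4.1.1 and the endpoint list call for one

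*Protocol*

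**What the plan says.** The protocol defines the trigger for the 3-Month Post-Injection Follow-Up Visit in several places.

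- Synopsis, Methodology: "Following each injection, subjects will return to the clinic for 3-Month Post-Injection Follow-Up Visits, unless another visit has occurred between the injection" (the interval ends at the 3-month date). Section 4.1 repeats this: "Following each injection, subjects will return to the clinic for 3-Month Post-Injection Follow-Up Visits".
- Section 4.1.1, General Injection Guidelines (repeated in the Synopsis): "Following each injection that occurs at or after the Month 3 visit, subjects will return to the clinic for a 3-Month Post-Injection Follow-Up Visit". Off-site glucocorticoid or HA injections given for OA are added. For an HA series, the first visit sets the follow-up date.
- Section 7.3.4: "This visit should occur 90 days after any Unscheduled Injection Visit or after any IA glucocorticoid or HA injection occurring at a location different" from the study site, with a window of ± 14 days.
- Section 7.3.7, footnote c: "This visit should occur 90 days after the Unscheduled Injection Visit or any IA glucocorticoid or HA injection occurring at a location different" from the study site, with the same window.

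Every version waives the visit if another visit falls between the injection and the 3-month date.

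Footnote g lists where injections may be given: "At Unscheduled Injection Visits, 3-Month Post-Injection Follow-Up Visits, or at Months 3, 12, or 24 (after completion of all visit assessments), subjects may receive". The products it names are glucocorticoid, HA and LOR. Sections 4.1.1, 7.3.3 and 7.3.4 agree. In Section 3.2.2, the pain NRS, WOMAC, KOOS, walk-test and TUG endpoints are to be assessed at Month 3, at the annual visits, "at each Unscheduled Injection Visit, and 3 months after each injection".

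**The concern.** Section 7.3.4 and footnote c give the visit its day count and window, and Section 4.1 sends the reader to the Schedule of Events for specific timing. A site that follows that direction reaches the narrowest trigger. It covers Unscheduled Injection Visits and off-site glucocorticoid or HA injections, but not an on-site injection given at Month 3, 12 or 24 or at a follow-up visit.

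Two things are at stake. Section 10.4.3 planned to characterize efficacy by medication and injection number, so the value about 3 months after an injection is a core item of data. Whether it exists would depend on the type of visit at which the injection was given and on which section the site followed. Second, Month 3 is the first time glucocorticoid or HA is allowed, and the primary objective covers LOR in addition to those treatments. A long gap after a Month 3 injection therefore delays the routine knee examination and AE query just when combined exposure can begin.

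**Working it through.** The plan states no figure for this point. The check compares the texts and then does day arithmetic on the protocol's own visit schedule.

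**Step 1. Which injections trigger the visit** (before the waiver, which is common to all versions)

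| Injection occasion | Synopsis Methodology, 4.1 | 4.1.1, Synopsis guidelines | 7.3.4, footnote c |
|---|---|---|---|
| Unscheduled Injection Visit before Month 3 (LOR only) | yes | no | yes |
| Unscheduled Injection Visit after Month 3 | yes | yes | yes |
| Month 3, 12 or 24 visit | yes | yes | **no** |
| 3-Month Post-Injection Follow-Up Visit | yes | yes | **no** |
| Off-site glucocorticoid or HA for OA | yes | yes | yes |

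The two **no** entries in the last column cannot be removed by treating such a visit as an Unscheduled Injection Visit, because Section 4.1.1 and footnote g list these as alternative visit types.

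**Step 2. Time to the next scheduled clinic visit after an omitted injection**

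Inputs (7.3.3 and 7.3.5): Month 3 = Day 90 ± 14; Month 12 = Day 360 ± 28; Month 24 = Day 720 ± 28; Month 36 = Day 1080 ± 28.

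Nominal gap = next day − injection day. Shortest gap = (next day − its window) − (injection day + its window). Longest gap = (next day + its window) − (injection day − its window).

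- Month 3 to 12: nominal 360 − 90 = 270; shortest 332 − 104 = 228; longest 388 − 76 = 312.
- Month 12 to 24: nominal 720 − 360 = 360; shortest 692 − 388 = 304; longest 748 − 332 = 416.
- Month 24 to 36: nominal 1080 − 720 = 360; shortest 1052 − 748 = 304; longest 1108 − 692 = 416.

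The upper limit of the 3-month window is 90 + 14 = 104 days. Even the shortest gap, 228 days, exceeds it, so no scheduled visit can stand in for the 3-month assessment. Follow-up visits have no fixed study day, so no single gap can be given for injections at those visits.

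**Step 3. Does the difference between 4.1 and 4.1.1 matter?**

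The two differ only for injections before the Month 3 visit. Let the injection be on Day d and the Month 3 visit on Day m, with m from 76 to 104. Section 4.1 waives the extra visit when d < m ≤ d + 90. The waiver fails only if m > d + 90.

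- If m ≤ 91, this would need d < 1, so the waiver always applies.
- If m is 92 to 104, it needs d ≤ m − 91, so d is at most 104 − 91 = 13.

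The two sections therefore part only for an injection on Days 1 to 13 followed by a Month 3 visit on Days 92 to 104. In those cases the Month 3 visit falls 91 to 103 days after the injection (m − d). That is within 90 ± 14, and the same measures are collected. The difference is almost purely one of wording.

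**The case against.** The strongest reply is that sites are sent to the wider rule. Where 7.3.3 and 7.3.4 permit an injection at Months 3, 12 and 24 or at a follow-up visit, they refer the reader to 4.1.1, and footnote g does the same. Section 4.1.1 holds the follow-up rule for each injection from Month 3 on. This stands in part: a site that follows the reference would book the visit. But the reference is given for injection restrictions and guidelines, while the passages that fix this visit's timing still say something narrower.

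A reader might infer three stronger points that the documents do not support.

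- *That there are three materially different triggers.* Step 3 shows that 4.1 and 4.1.1 hardly differ once the waiver is applied. The conflict that matters is 7.3.4 and footnote c against the rest.
- *That every injection at Months 3, 12 and 24 loses its 3-month value.* What follows is only that no such value is planned under the narrow rule. A site using 4.1.1, or an incidental visit, could still supply one.
- *That adverse events would go unrecorded.* Section 7.1.1 has events since the previous visit queried at each visit and allows a subject to be recalled between visits. Section 8.4.2 requires SAEs within 24 hours of site knowledge. The routine query is later, not absent.

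The consequence for this study is also small. There are no formal hypotheses (10.2), and the SAP lists efficacy data without analyzing them (SAP 5.1 and 7). SAP 8.2 says no subject completed a post-baseline laboratory visit. The protocol takes those samples from Month 12 on, so this suggests, without stating it, that Month 12 and 24 injections did not occur.

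**Conclusion.** The inconsistency is real and should be corrected. Read as written, 7.3.4 and footnote c leave on-site injections at Months 3, 12 and 24 and at follow-up visits with no planned 3-month assessment. The other sections and the endpoint list call for one. For the three fixed visits, the shortfall is a next scheduled clinic contact at 270 or 360 days instead of 90.

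This rests on two assumptions: that a site follows the narrow text alone, and that no other visit happens to intervene. The documents do not say how many sites did so, or how many injections were given at such visits. In the study as it ended, probably only injections at Month 3 or at follow-up visits could have been affected. The point concerns the protocol's consistency and the reading of the listings; no reported analysis changes.

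**What to change.** Use one trigger, consistent with the endpoint list, in all six places: the two Synopsis passages, 4.1, 4.1.1, 7.3.4 and footnote c. It should expressly cover on-site injections at Months 3, 12 and 24 and at follow-up visits. The same edit should:

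- state whether the waiver for an intervening visit stays, since while it stays some injections before Month 3 will still be assessed earlier than 3 months after the injection;
- keep the rule that the first visit of an HA series sets the follow-up date, so that a series does not generate several follow-up visits;
- settle whether the off-site trigger is limited to injections for OA, as in 4.1.1, or unrestricted, as in 7.3.4 and footnote c.

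The cost is wording. If the waiver stays, no visits are added beyond those that 4.1 and 4.1.1 already promise. If it is dropped, visits are added and should be counted.

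Because the study has ended, the practical step is in reporting. The efficacy listings should say which trigger was applied, so that an absent 3-month record can be read as not scheduled or as missed. The protocol text should be corrected before it is reused.

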7.3.5 FINAL STUDY VISIT

Month 36 End of Study

The Month 36 visit should occur on Day 1080 (with a window of ± 28 days).

The following procedures and assessments will be performed at this visit:

- Collection of AE and concomitant procedures/therapies/medication data
- Physical examination, including knee examination of both knees
- Weight measurement
- Pregnancy test (urine-based) for WOCBP
- Vital sign measurements (temperature, pulse rate, and blood pressure)
- WOMAC questionnaire
- KOOS questionnaire
- Pain NRS
- SF-12 questionnaire
- PASS questionnaire
- WPAI questionnaire
- 40-meter walk test (at a subset of sites)
- TUG test (at a subset of sites)
- Collection of samples for clinical laboratory tests

7.3.6 EARLY TERMINATION VISIT

If possible, the following procedures and assessments should be performed within 14 days of subject premature withdrawal or termination.

- Collection of AE and concomitant procedures/therapies/medication data
- Physical examination, including knee examination of both knees
- Weight measurement
- Pregnancy test (urine-based) for WOCBP
- Vital sign measurements (temperature, pulse rate, and blood pressure)

- WOMAC questionnaire
- KOOS questionnaire
- Pain NRS
- SF-12 questionnaire
- PASS questionnaire
- WPAI questionnaire
- 40-meter walk test (at a subset of sites)
- TUG test (at a subset of sites)
- Collection of samples for clinical laboratory tests

Note: PRO measurements (WOMAC, KOOS, pain NRS, SF-12, PASS, WPAI) and functional tests (40-meter walk test and TUG test) do not need to be completed at this visit if they were completed within 2 weeks prior.

7.3.7 SCHEDULE OF EVENTS TABLE

Schedule of Study Procedures	Screening (Day -14 to Day -1)	Day 1^a	Month 1 (Phone) (Day 30 ± 7 days)	Month 3 (Day 90 ± 14 days)	Months 12 and 24 (Days 360 and 720 ± 28 days)	Unscheduled Injection Visit^b	3-Month Post- Injection Follow-Up Visit^c (± 14 days)	Month 36 (EOS) (Day 1080 ± 28 days)/ ET^d
Informed consent	X							
Inclusion & exclusion criteria	X	X						
Demographics	X							
Medical history	X							X ^e
Current and prior procedures/medications	X	X						
Past treatments for knee OA pain	X							
Pregnancy test ^f	X	X						X
Urine drug test	X							
Injection into knee ^g		X ^h				X		
Physical examination	X	X			X			X
Knee examination	X	X		X	X	X	X	X
Weight	X				X			X
Height	X							
Vital signs	X	X		X	X	X	X	X
Clinical laboratory sampling	X				X			X
WPI&SS		X						
Charlson Comorbidity Index		X						
WOMAC		X		X	X	X	X	X
KOOS		X		X	X	X	X	X
Pain NRS		X		X	X	X	X	X

Schedule of Study Procedures	Screening (Day -14 to Day -1)	Day 1^a	Month 1 (Phone) (Day 30 ± 7 days)	Month 3 (Day 90 ± 14 days)	Months 12 and 24 (Days 360 and 720 ± 28 days)	Unscheduled Injection Visit^b	3-Month Post- Injection Follow-Up Visit^c (± 14 days)	Month 36 (EOS) (Day 1080 ± 28 days)/ ET^d
SF-12		X		X	X			X
PASS Question		X		X	X			X
WPAI		X		X	X			X
40-meter walk test ⁱ		X		X	X	X	X	X
TUG test ⁱ		X		X	X	X	X	X
AEs & concomitant procedures/ therapies/medications		X	X	X	X	X	X	X

- ^a All Day 1 procedures should be performed prior to study medication injection except for collection of AE and concomitant procedures/medication data.
- ^b The Unscheduled Injection Visit may only occur between Day 1 and Month 33 if the subject is receiving an IA LOR injection, or between Month 3 and Month 33 if the subject is receiving an IA glucocorticoid or HA injection. PRO measurements (WOMAC, KOOS, and pain NRS) and functional tests (40-meter walk test and TUG test) do not need to be completed at the Unscheduled Injection Visit if they were completed within 2 weeks prior.
- ^c This visit should occur 90 days after the Unscheduled Injection Visit or any IA glucocorticoid or HA injection occurring at a location different than the study site (with a window of ± 14 days) unless another visit has occurred between the injection and the 3-month post injection date.
- ^d If possible, the ET visit should be performed within 14 days of subject premature withdrawal or termination. PRO measurements (WOMAC, KOOS, pain NRS, SF-12, PASS, WPAI) and functional tests (40-meter walk test and TUG test) do not need to be completed at the ET visit if they were completed within 2 weeks prior.
- ^e Review medical history to capture End Date(s), if applicable, of any ongoing medical history(ies) collected at the Screening Visit.
- ^f A serum pregnancy test will be performed on WOCBP at the Screening visit and a urine pregnancy test will be performed on WOCBP at Day 1 and Month 36 (EOS)/ET.
- ^g At Unscheduled Injection Visits, 3-Month Post-Injection Follow-Up Visits, or at Months 3, 12, or 24 (after completion of all visit assessments), subjects may receive LOR, glucocorticoid, or HA in either knee. Refer to the OA Treatment Algorithm in [Section 4.1.1](#) for further details.
- ^h Subjects are to receive an IA injection of LOR into one or both knees on Day 1.
- ⁱ Functional tests will only be performed at a subset of sites.
- ^j For any subjects who have a total or partial knee replacement of the knee diagnosed with OA in unilateral OA or of either knee in bilateral OA, sites should follow up with these subjects approximately 6 months after the total or partial knee replacement surgery is completed to assess outcomes of the surgery.

